## **Research Design & Methods:**

All patients meeting the inclusion criteria will be offered enrollment into the study. Cases will be collected over a 6 – 18 months interval.

Although there will be no direct benefit or anticipated impact on the care of patients enrolled in this study, it is reasonable to expect that the results will prove beneficial to patients undergoing spine surgery in the future.

## **Patient Enrollment:**

Every steps outlined below are mandatory and must be adhered to for successful patient enrollment into study:

- For the 4 cohorts
  - a. Signed consent
  - b. Complete preoperative data (planning)
  - c. Surgical treatment
  - d. Complete surgical data
  - e. Complete postoperative data

Post-operative acquisitions will be performed at one week and then 3-4 months after the surgery.

## **Data Collection:**

The data form(s) to be utilized for the purpose of collecting specific data and will not contain patient identifiable information. Data collection schedule as follows:

Current practice planning	Preop	Periop	1 week Post op	3–4 months post-op
Patient Demographics	X			X
HRQL Questionnaires/Pain Tools (SRS22r, SF-12, ODI, NDI, EQ5D)	X			X
Clinical Exam	X			X
3D modeling				
Radiographic Data (Coronal & Sagittal EOS Films)	X		X	X
Surgical Data		X		
2D Planning questionnaire	X			
3D Planning questionnaire				
Surgical questionnaire		X		
Post-op questionnaire (2 questionnaires)			X	

Current practice planning + 3D parameters from 3D modeling	Preop	Periop	1 week Post op	3–4 months post-op
Patient Demographics	X			X
HRQL Questionnaires/Pain Tools (SRS22r, SF-12, ODI, NDI, EQ5D)	X			X
Clinical Exam	X			X
3D modeling	X			
Radiographic Data (Coronal & Sagittal EOS Films)	X		X	X
Surgical Data		X		
2D Planning questionnaire	X			
3D Planning questionnaire	X			
Surgical questionnaire		X		
Post-op questionnaires (2 questionnaires)			X	

All available information from the original source documents will be centralized into global spreadsheets in order to perform the preliminary and final analyses.

## DATA MANAGEMENT AND ANALYSIS

---

### Demographic and HRQOL (see appendix 1)

Demographic data (Age, Weight, Height,...), Health Related Quality Of Life (HRQOL) data, and pain diagram data (VAS) will be collected in order to quantify the subjects' self-reported pain, level of disability and physical activity.

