## STUDY DESIGN

---

The study will be prospective, randomized, occurring in New-York Presbyterian Hospital. The study design includes 4 arms:

- Cohort A: Adults and standard of care (EOS biplane acquisition). Planning performed with current practice.
- Cohort B: Adults and standard of care (EOS biplane acquisition). Planning performed with additional 3D information provided by 3D modeling on sterEOS software (FDA approved)
- Cohort C: Children and standard of care (EOS biplane acquisition). Planning performed with current practice.
- Cohort D: Children and standard of care (EOS biplane acquisition). Planning performed with additional 3D information provided by 3D modeling on sterEOS software (FDA approved)

For cohort B and D, 3D additional information will be provided to the surgeons. This information may help them to better understand the pathology and plan the procedure.

Radiographic, clinical parameters and freeform observations by the surgeon will be collected at pre-operative, peri-operative and post-operative steps, for patients who meet the inclusion criteria and signed the informed consent. The recorded parameters and freeform observations will be compared between patients of cohort A and B, and cohort C and D.

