### Radiographic data

A full-length EOS exam from head to feet will be performed in the standing position. De-identified images will be transferred to the EOS 3D services through the 3D Services Platform (<https://eos3dservices.com/>). Trained and skilled technicians will perform the 3D reconstructions of the spine, the pelvis and lower extremities, using spine workflow and global Postural Assessment workflow on sterEOS software. 3D models will be made available for visualization and validation by the surgeons in the spineEOS software, which is available through the 3D Services Platform (FDA-approved, HIPAA-compliant). 2D parameters will be obtained in the actual standard of care.

- **2D parameters**

- Sagittal plane
  - Pelvic Incidence, Pelvic Tilt, Sacral Slope
  - Lumbar lordosis (L1-S1 and maximal)
  - Thoracic kyphosis (T4-T12 and maximal)
  - Thoraco-lumbar alignment
  - Cervical alignment
  - T1 and T9 spino-pelvic inclination
  - Retro and spondylolisthesis
  - C7SVA
  - Global Cranial-Hip and Cranial-Ankle alignment
- Coronal plane
  - Cobb angles
  - Rotatory subluxations
  - C7 plumbline
  - AVT Thoracic
  - AVT Lumbar

- **3D parameters**

- Same parameters described in 2D but also measured in 3D
- Vertebrae orientations in the three planes
- Intervertebral rotations in the three planes
- Sagittal balance parameters : SVA, CAM-HA, Spino sacral angle, T1 and T9 tilt, FBI
- ...

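### No masking is specified, although paired cohorts differ only in the 3D information given to surgeons, so knowledge of the cohort could colour self-reported scores and 2D film readings

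*Combined protocol and SAP*

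**What the plan says.** **Allocation and comparison.** Study Design states: "The study will be prospective, randomized, occurring in New-York Presbyterian Hospital". It also says: "The recorded parameters and freeform observations will be compared between patients of cohort A and B, and cohort C and D".

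**What differs between cohorts.** The adult control cohort is described as "Cohort A: Adults and standard of care (EOS biplane acquisition). Planning performed with current practice", and its counterpart as "Cohort B: Adults and standard of care (EOS biplane acquisition). Planning performed with additional 3D information provided by 3D modeling on sterEOS software". Cohorts C and D repeat this for children; C reads "Children and standard of care (EOS biplane acquisition). Planning performed with current practice". The 3D material goes to one group of people: "For cohort B and D, 3D additional information will be provided to the surgeons". Radiographic data likewise makes the models available to surgeons for viewing and validation.

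**Schedule.** The two tables in Data Collection differ only before surgery, in the 3D modeling row and the 3D planning questionnaire row. Both have the health-related quality of life (HRQL) instruments (SRS22r, SF-12, ODI, NDI, EQ5D) before surgery and at 3-4 months, and films before surgery, at 1 week and at 3-4 months.

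**Outcomes open to influence.** Demographic and HRQOL adds a VAS pain diagram and gives the aim as quantifying "self-reported pain, level of disability and physical activity". For film measurements, Radiographic data says "2D parameters will be obtained in the actual standard of care".

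**Masking.** The design, data collection, radiographic and analysis sections say nothing about masking patients, film measurers or analysts. De-identification is described for transfer of images to the 3D service and for privacy, not for concealing the cohort.

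**The concern.** Scores for pain, disability and quality of life depend on what patients believe about their treatment. A patient who knows that the operation was planned with extra 3D information may expect, and report, a better result. Manual angle and alignment measurements leave some room for judgement, and a measurer who knows the cohort can lean one way without intending to. Either effect would look like a benefit of 3D planning, and neither can be removed once the data are collected.

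The design makes patient masking unusually easy. Imaging and postoperative visits are the same within each pair, so a patient has no evident way of identifying the cohort except by being told it or shown the model. No sham procedure, extra image or extra visit would be needed. The protocol does not take up this opportunity.

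**Working it through.** The plan has no figure to reproduce here. It gives no effect size, SD, power or allocation ratio, so what follows is an illustration and not a recalculation.

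**Step 1: could knowledge of the cohort affect the planned comparison?**

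| Feature | A / C | B / D |
|---|---|---|
| EOS biplane acquisition | yes | yes |
| 3D modeling and 3D planning questionnaire (before surgery) | no | yes |
| HRQL before surgery and at 3-4 months | yes | yes |
| Films before surgery, at 1 week and at 3-4 months | yes | yes |
| Recipient of the 3D information | none | surgeon |

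The surgeon must know the cohort; the patient need not. The 3D rows apply only before surgery and only in B and D, so the film readings that can be compared between cohorts are the 2D ones.

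**Step 2: inputs for the illustration.**
- Total enrolment: around 160 (Number of Subjects). The split is not stated. Assumed 160/4 = 40 per cohort, with 30 as a lower case.
- Significance level: 0.05 (Data Analysis and Data Monitoring). Two-sided is assumed.
- Test: a comparison of two cohort means, normal approximation, SD scaled to 1. This is assumed.
- Reporting or reading bias b, in SD units: assumed 0.1, 0.2 and 0.3, with no true effect.

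**Step 3: formula.** The standard error of the standardised difference is SE = √(2/n). With no true effect and bias b,

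P(nominal significance) = Φ(b/SE − 1.96) + Φ(−b/SE − 1.96).

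**Step 4: numbers at 40 per cohort.** SE = √(2/40) = 0.224.
- b = 0: 5.0%.
- b = 0.1: b/SE = 0.447; 0.0652 + 0.0080 = 7.3%.
- b = 0.2: b/SE = 0.894; 0.1433 + 0.0022 = 14.6% (0.1455 before rounding).
- b = 0.3: b/SE = 1.342; 0.2682 + 0.0005 = 26.9%.

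At 30 per cohort, SE = √(2/30) = 0.258 and the results are 6.7%, 12.1% and 21.3%.

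**Step 5: without a test.** If the cohorts are compared only by their means, the bias b passes in full into the observed difference. The concern therefore does not depend on a significance test; only the percentages do.

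**The case against.** The strongest reply is that much of this rests on silence and on assumed inputs. Several parts of that reply stand.

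- **No between-cohort test is specified.** Data Analysis and Data Monitoring gives HRQL data descriptive statistics and names Student's t-test only for the significance of correlations. HRQL falls within the comparison in Study Design only if it counts among the recorded or clinical parameters. The percentages therefore describe an assumed test.
- **Pooling adults and children.** A reader might combine the age groups, 80 against 80, and obtain 24% and 48% for biases of 0.2 and 0.3 SD. The documents do not support this: they plan two separate comparisons.
- **Do patients know their cohort?** A reader might infer that they are told. The documents do not say so, and the consent pages were not available for review.
- **Do film measurers know the cohort?** A reader might infer that the treating team measures the films with that knowledge. Radiographic data refers only to standard of care; it does not say who measures or what they know.
- **Is masking free?** For patients it needs no added imaging or visit. For films, a separate reader covering a long parameter list at two postoperative visits would be new work.
- **The study is a pilot.** It describes itself as largely observational and names no primary endpoint. Surgeon questionnaires and freeform observations are central to it, and those cannot be masked.

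These points limit the size and certainty of the concern. They do not remove it: the cohorts are randomised, a comparison is planned, the instruments are subjective, and the sections where masking of patients or measurers would be expected do not mention it.

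**Conclusion.** The concern holds as a risk, not as a demonstrated bias. The supplied protocol sets no masking in a randomised comparison where patients could readily be kept unaware of their cohort and where self-reported scores and 2D readings could be influenced by knowing it.

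Its size is illustrative: about 7%, 15% or 27% nominal significance instead of 5% for biases of 0.1, 0.2 or 0.3 SD. This rests on four assumptions outside the plan: the size of the bias, 40 per cohort, a two-sided test of cohort means, and no true effect. The documents give no basis for choosing among the bias values.

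The case for acting rests on the small cost of the change rather than on those percentages. Masking would protect the HRQL and VAS scores and, where it can be arranged, the 2D measurements. It would not protect the surgeon-reported data.

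**What to change.** **Patients.** Add to Study Design and Data Collection: *Patients and families are told that the planning method is randomised, but are not told the cohort or shown the 3D model until the 3-4 month questionnaires are complete.* The consent wording should agree with this.

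**Surgeons.** State that surgeons are unmasked, and that their questionnaires and freeform observations are to be read as unmasked data.

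**Films.** Where existing staff measure the postoperative 2D parameters, withhold the cohort code from the films they work on. No added reader is proposed. If the measurer is a surgeon who already knows the cohort, say so, since removing the code would then achieve little.

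**Cost.** A few sentences of text and leaving the code off the films; no extra visits, imaging or sample size. Surgeons must refrain from showing patients the model for 3-4 months. Masking may still be incomplete, because surgeons know the cohort and could disclose it.

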### Radiographic data

A full-length EOS exam from head to feet will be performed in the standing position. De-identified images will be transferred to the EOS 3D services through the 3D Services Platform (<https://eos3dservices.com/>). Trained and skilled technicians will perform the 3D reconstructions of the spine, the pelvis and lower extremities, using spine workflow and global Postural Assessment workflow on sterEOS software. 3D models will be made available for visualization and validation by the surgeons in the spineEOS software, which is available through the 3D Services Platform (FDA-approved, HIPAA-compliant). 2D parameters will be obtained in the actual standard of care.

- **2D parameters**

- Sagittal plane
  - Pelvic Incidence, Pelvic Tilt, Sacral Slope
  - Lumbar lordosis (L1-S1 and maximal)
  - Thoracic kyphosis (T4-T12 and maximal)
  - Thoraco-lumbar alignment
  - Cervical alignment
  - T1 and T9 spino-pelvic inclination
  - Retro and spondylolisthesis
  - C7SVA
  - Global Cranial-Hip and Cranial-Ankle alignment
- Coronal plane
  - Cobb angles
  - Rotatory subluxations
  - C7 plumbline
  - AVT Thoracic
  - AVT Lumbar

- **3D parameters**

- Same parameters described in 2D but also measured in 3D
- Vertebrae orientations in the three planes
- Intervertebral rotations in the three planes
- Sagittal balance parameters : SVA, CAM-HA, Spino sacral angle, T1 and T9 tilt, FBI
- ...

## **Data Analysis and Data Monitoring**

This pilot study is mainly an observational study. The aim of the study is only to observe the value of additional information provided by 3D modeling with sterEOS software.

At the end of the 6 first months of the study, a first data analysis will be performed at Columbia with the available data in order to have some preliminary results. The final data analysis will be performed at the end of the data collection, when every patients enrolled will have the full assessment (preop, periop and post-op data). This analysis will be performed at EOS Imaging with the shared data provided by Columbia.

Descriptive analysis (mean, range and standard deviations) will be calculated for all the parameters and HRQOL data with Excel software. Correlations will be performed using Pearson correlation coefficient, and Student's t-Test will be utilized to determine if these correlations are significant, with significant p-value set at 0.05.

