### Number of Subjects

Every patient with spinal deformity meeting the inclusion criteria will be enrolled in this prospective pilot study. Around 160 subjects are anticipated to enroll in the project. Patients with spinal deformity will be identified during office hours of [name] for adults and pediatrics, [name] for Adults and pediatrics, and [name], [name] and [name] for pediatrics. Patient will be segregated between the different cohort regarding their age (A and B for adults, C and D for children).

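### The promised A-versus-B and C-versus-D comparisons have no specified between-cohort estimate, and the pre-operative HRQL and 2D radiographic values collected in every cohort are given no role in one

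*Combined protocol and SAP*

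**What the plan says.** Under Study Design: "The study will be prospective, randomized, occurring in New-York Presbyterian Hospital". The same section states: "The study design includes 4 arms". Cohorts A and B are adults, C and D are children, and B and D receive planning with added 3D information. It then commits to a comparison: "The recorded parameters and freeform observations will be compared between patients of cohort A and B, and cohort C and D".

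Both schedule tables under Data Collection, one for current-practice planning and one for planning with 3D parameters, mark the HRQL instruments ("SRS22r, SF-12, ODI, NDI, EQ5D") pre-operatively and again at 3–4 months. Both mark the radiographic data ("Coronal & Sagittal EOS Films") pre-operatively, at one week and at 3–4 months. Patient Enrollment makes complete pre-operative data mandatory in all four cohorts.

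Under Data Analysis and Data Monitoring, the plan for these data is: "Descriptive analysis (mean, range and standard deviations) will be calculated for all the parameters and HRQOL data with Excel software". The only inferential method named is the Pearson correlation; Student's t-test is assigned to judging those correlations at the 0.05 level. No regression, change score, stratified analysis or between-cohort test appears anywhere.

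On size, Number of Subjects says: "Around 160 subjects are anticipated to enroll in the project". No allocation ratio, effect size, SD or pre-post correlation is given.

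**The concern.** The comparison of A with B and of C with D is what the randomised layout exists to support, yet the analysis section does not say how it will be made. Two things are missing: an estimate of the cohort difference with its uncertainty, and a role for the pre-operative value, which is available for every patient at no extra cost.

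This matters because the cohorts are small. A pre-operative difference between two cohorts carries through to the post-operative difference in proportion to the pre-post correlation. It could be read as an effect of 3D planning or could hide one. Even with no such difference, an interval that ignores the pre-operative value is wider than the collected data require.

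**Working it through.** The plan states no precision or power figure, so there is nothing to reproduce. The calculation below is an illustration.

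**Inputs**
- Total of about 160 in 4 cohorts (Number of Subjects; Study Design). Assumed equal split: 160 / 4 = 40 per cohort.
- Outcome SD within cohort scaled to 1, assumed equal before and after surgery.
- Within-cohort pre-post correlation ρ: not in the documents; taken as 0.3, 0.5 and 0.7.
- Two-sided 95% intervals, normal approximation.

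**Unadjusted difference**

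SE = √(2/40) = 0.224 SD. Half-width = 1.96 × 0.224 = 0.44 SD.

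**Adjusted for the pre-operative value**

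The variance is multiplied by 1 − ρ², so the half-width is 1.96 × √[(2/40)(1 − ρ²)]. The equivalent unadjusted cohort size is 40 / (1 − ρ²).

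| ρ | 1 − ρ² | SE (SD) | 95% half-width (SD) | Equivalent unadjusted n per cohort |
|---|---|---|---|---|
| 0 (unadjusted) | 1.00 | 0.224 | 0.44 | 40 |
| 0.3 | 0.91 | 0.213 | 0.42 | 44 |
| 0.5 | 0.75 | 0.194 | 0.38 | 53 |
| 0.7 | 0.51 | 0.160 | 0.31 | 78 |

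**Why regression and not a simple change score**

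The change score has variance factor 2(1 − ρ): 1.4, 1.0 and 0.6 at ρ = 0.3, 0.5 and 0.7. Regression gives 0.91, 0.75 and 0.51. At ρ = 0.3 the change score is less precise than ignoring the pre-operative value altogether.

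**Chance imbalance under clean randomisation, 40 versus 40**

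P(|pre-operative difference| > 0.3 SD) = 2[1 − Φ(0.3 / 0.224)] = 0.18 for any one measure. A 0.3 SD imbalance moves an unadjusted post-operative difference by 0.3ρ, that is 0.09, 0.15 or 0.21 SD.

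**Where this does and does not apply**

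- It applies to HRQL scores and continuous 2D radiographic values, which are measured before and after surgery in both cohorts of each pair.
- It does not apply to the 3D parameters. 3D modeling has no mark in the current-practice table and only a pre-operative mark in the other.
- It does not apply to surgical data or to the surgical and post-op questionnaires, which have no pre-operative value.

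**The case against.** **The study is a pilot that calls itself mainly observational.** This stands, and it limits the weight of the point. There is no primary endpoint and no cohort test at 0.05 to invalidate. A pilot meant to show where 3D information helps still benefits from tighter, interpretable estimates.

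**A reader might infer that the plan will compare raw post-operative means.** The documents do not say so. The descriptive statistics are not tied to a time point, and the t-test is for correlations. What can be said is that no between-cohort method is given; adjustment is the second half of the repair.

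**The gain depends on an unknown correlation.** This stands. Surgery acts directly on alignment, so ρ for radiographic values could be low. At 0.3 the half-width shrinks only from 0.44 to 0.42 SD.

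**A reader might take the 18% as describing imbalance in this trial.** It assumes clean randomisation. The note closing the children's EOS exclusion criteria sends every patient who meets only those criteria to A (adults) or C (children). That movement is not random and always goes into the control cohorts, so part of any imbalance may be systematic. Regression on the pre-operative value would correct it only in part.

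**A reader might want one combined adult-and-child estimate and credit its precision to adjustment.** Pooling 80 versus 80 without adjustment already gives 1.96 × √(2/80) = 0.31 SD; adjusting at ρ = 0.6 takes it to 0.25 SD. Most of the fall from 0.44 SD therefore comes from pooling. The plan deliberately keeps the two age groups apart, and stratified randomisation is nowhere stated. Such an estimate is an optional summary, and its absence is not a defect.

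**Conclusion.** The point holds in limited form. The documents promise two between-cohort comparisons and collect the pre-operative values that would sharpen them. They specify neither an estimate of the cohort difference nor any use of those values.

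With 40 per cohort and ρ of 0.3, 0.5 or 0.7, adjustment reduces the variance of the difference by 9%, 25% or 49%, and the 95% half-width falls from 0.44 SD to about 0.42, 0.38 or 0.31 SD. The equal split and the correlations are assumptions.

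The gain is in precision and interpretability, for HRQL and 2D radiographic values only. The documents do not support the stronger reading that an invalid confirmatory test is planned.

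**What to change.** In Data Analysis and Data Monitoring, add the following.

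1. For each HRQL score and each continuous 2D radiographic value at 3–4 months, estimate the 3D-minus-control difference with a 95% confidence interval. Use linear regression on cohort, with the patient's own pre-operative value as covariate. Fit it separately for adults (A versus B) and children (C versus D).
2. Leave patients moved to A or C under the EOS-exclusion note out of this comparison, or report them separately, because they were not randomly assigned. Apply the EOS criteria in the same way to both cohorts of a pair, so that the patients who remain are comparable.
3. State that 3D parameters, surgical data and the surgical and post-op questionnaires are outside this model and remain descriptive.
4. Optionally, give a combined estimate stratified by age group as a secondary summary beside the separate results.

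The cost is a paragraph of analysis text and a regression routine in addition to spreadsheet summaries. No further patients, visits or measurements are needed. Omitting the transferred patients makes the control cohorts in this comparison smaller, by a number the documents do not allow one to estimate.

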### Our hypothesis is that:

1. 3D parameters could bring additional information in pre-operative, surgery and post-op control.

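### The randomized A-vs-B and C-vs-D comparisons have no planned effect estimate or interval, and a test of a single Pearson correlation cannot show what a 3D parameter adds to its own 2D version

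*Combined protocol and SAP*

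**What the plan says.** The Study Design section states "The study will be prospective, randomized" and then "The recorded parameters and freeform observations will be compared between patients of cohort A and B, and cohort C and D". The hypothesis is that "3D parameters could bring additional information in pre-operative, surgery and post-op control", and the analysis section repeats the idea: "The aim of the study is only to observe the value of additional information provided by 3D modeling with sterEOS software".

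The whole analysis plan is in Data Analysis and Data Monitoring. It has a descriptive part, "Descriptive analysis (mean, range and standard deviations) will be calculated for all the parameters and HRQOL data with Excel software", and an inferential part, "Correlations will be performed using Pearson correlation coefficient", for which a Student's t-test "will be utilized to determine if these correlations are significant, with significant p-value set at 0.05". The t-test is attached to the correlations, not to the arms. The section does not say which variables are correlated, whether the descriptive statistics are tabulated by cohort, or which difference or interval will describe A against B or C against D.

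Three other places bear on the point:
- **Radiographic data.** The 3D list starts by repeating the 2D parameters, then adds items such as vertebral orientations and intervertebral rotations.
- **Note after the children's EOS exclusion criteria.** Patients who meet only an EOS exclusion are moved automatically to A (adults) or C (children).
- **Data Collection tables.** 3D modeling is marked only pre-operatively and only in the 3D-planning arms. Those arms complete both a 2D and a 3D planning questionnaire pre-operatively; the current-practice arms complete only the 2D one.

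**The concern.** The comparison that randomization would support, and that bears most directly on the value of giving surgeons 3D information, has no stated effect measure. The only p-values planned belong to correlations, which do not compare arms.

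Two things are at stake. First, if the cohorts are compared as they end up, A and C contain patients who could never have been in B or D. Children under 7, for example, can appear only in C. A difference between C and D would then mix the effect of 3D planning with age and anatomy. Second, the reader of a significant 3D correlation could not tell whether 3D contributed something or repeated what the 2D measurement already showed. The final analysis is to be done at EOS Imaging, whose system is being assessed, so it matters more that the choice of comparisons is written down beforehand.

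**Working it through.** **Inputs from the documents.** Total enrolment: "Around 160 subjects are anticipated to enroll in the project" (Number of Subjects). Significance level 0.05 (Data Analysis and Data Monitoring). The 160 cannot be reproduced, because no effect size, SD, power, allocation ratio or dropout is given with it.

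**Assumptions not in the documents.** Equal split, 160/4 = 40 per cohort; two-sided test of r = 0 (the usual meaning of a t-test of a correlation; the null value is not written); normal data; all correlations used below.

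**Step 1. What the arm comparison could deliver.** The 95% half-width of a difference in means, in SD units, is t × √(1/n₁ + 1/n₂).
- 40 vs 40: 1.991 × √(2/40) = 0.445
- 30 vs 30: 0.517; 50 vs 50: 0.397; 20 vs 20: 0.64
- Unequal, 60 vs 20: 0.514

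**Step 2. What a significant correlation means.** The critical value is r = t/√(n − 2 + t²). At n = 40 it is 2.024/√(38 + 4.10) = 0.312.
- *If the pair is 2D with 3D:* an assumed r of 0.9 gives t = 0.9 × √38/√(1 − 0.81) = 12.7. This is significant, but shows only that the two versions overlap.
- *If the pair is 3D with an outcome:* suppose 3D adds nothing once 2D is known. Its correlation with the outcome is then r(2D,outcome) × r(2D,3D). That is attenuated but not zero: 0.4 × 0.5 = 0.20, and 0.4 × 0.95 = 0.38.

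**Step 3. How often the test is significant** (40,000 simulated datasets per setting, n = 40):

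| r(2D,3D), assumed | 0.3 | 0.5 | 0.7 | 0.8 | 0.9 | 0.95 |
|---|---|---|---|---|---|---|
| Plain test, 3D adds nothing, r(2D,outcome) = 0.4 | 0.115 | 0.237 | 0.427 | 0.533 | 0.640 | 0.693 |
| Plain test, 3D adds nothing, r(2D,outcome) = 0.3 | 0.086 | 0.150 | 0.256 | 0.323 | 0.400 | 0.435 |
| Plain test, outcome depends on 3D only, r = 0.4 | 0.74 | 0.74 | 0.74 | 0.74 | 0.74 | 0.74 |
| Test adjusted for 2D, 3D adds nothing | 0.05 | 0.05 | 0.05 | 0.05 | 0.05 | 0.05 |
| Test adjusted for 2D, outcome depends on 3D only, r = 0.4 | 0.697 | 0.612 | 0.465 | 0.347 | 0.204 | 0.131 |

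(Rows three and four are rounded; the simulated values were 0.741–0.746 and 0.048–0.053.) At r(2D,3D) = 0.9 the plain test is significant in 64% of runs with nothing added and 74% with everything coming from 3D. At 0.5 it separates the two cases better, 24% against 74%.

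**Step 4. Limit of the adjusted test.** The 5% holds when the outcome follows the observed 2D reading. Suppose instead that 2D and 3D are equally noisy readings of the same anatomy, each with r = 0.4 to the outcome. The partial correlation is then (0.4 − 0.4q)/√((1 − 0.16)(1 − q²)) with q = r(2D,3D), which is 0.25 at q = 0.5 and 0.10 at q = 0.9. The adjusted test rejects in about 34–35%, 14%, 9–10% and 7% of runs at q = 0.5, 0.8, 0.9 and 0.95.

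**Step 5. Precision of the adjusted estimate.** The half-width near zero is tanh(1.96/√(n − 4)), which is 0.316 at n = 40 and 0.221 at n = 80 (B and D pooled). Adjusting also for age group gives tanh(1.96/√75) = 0.22.

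**The case against.** The strongest case against runs as follows. The study is labelled a pilot and mostly observational, so formal comparisons may not be expected. No variable pairs are named, so Step 3 simulates an analysis the plan does not spell out, with correlations the plan does not give. The protocol's idea of additional information is what surgeons receive when planning, not prediction of outcome beyond 2D. Means and SDs, if tabulated by cohort, would let a reader derive a difference and an interval. The adjusted analysis is weakest exactly where 2D and 3D are closest: 20% detection at r(2D,3D) = 0.9 with n = 40.

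Much of this stands, and it sets the order of priority. The percentages are an illustration, large only when 2D and 3D are closely related. The adjusted analysis belongs second, because the arm comparison is nearer to what the protocol means by value. A changed plan in B or D has no control, since A and C complete no second planning questionnaire.

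What does not stand is the pilot label as a reason to leave the randomized comparison without an estimate. It excuses the absence of a power calculation, but intervals are what a pilot should report. Nor does leaving the pairs unnamed help: neither pairing considered above adjusts for the 2D version.

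**Conclusion.** The point holds as a gap in the analysis section that should be closed. The arm comparison announced in the design has no difference or interval; the cohorts as formed include patients placed by rule rather than by chance; and a single-correlation test does not address added information for 3D parameters that have a 2D counterpart. The arm half-width of about 0.45 SD rests on an assumed 40 randomized patients per arm. The 24% to 69% rests on a 3D-versus-outcome pairing, an assumed r(2D,outcome) of 0.4, n = 40 and an assumed r(2D,3D) of 0.5 to 0.95.

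A reader might infer more, and the documents do not support it:
- *That correlations are uninformative for every 3D parameter.* The argument does not reach those without a 2D version, such as vertebral orientations or intervertebral rotations.
- *That the trial will produce false claims at the simulated rates.* Neither the pairs nor the 2D–3D correlations are stated.
- *That the arm comparison is absent or unrecoverable.* It is announced, and the descriptive statistics give it a partial basis.
- *That a positive 2D-adjusted result would prove added value.* Step 4 shows it may partly reflect a second noisy reading of the same anatomy.

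**What to change.** Revise Data Analysis and Data Monitoring as follows.

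1. **Main analysis.** Report A-vs-B and C-vs-D differences with 95% confidence intervals, within age group, for measures scheduled in both arms: HRQL change from pre-op to 3–4 months, post-op 2D radiographic parameters, and surgical data. Name the measures. 3D parameters cannot be compared between arms, because they are scheduled only in B and D. Include randomized patients by allocated arm, and report separately those placed in A or C under the EOS-exclusion note without randomization.
2. **Secondary analysis in B and D.** For 3D parameters with a 2D counterpart, report the association with a named outcome, adjusted for the 2D value and age group, with a 95% interval. State that it is imprecise when 2D and 3D are highly correlated, that non-significance does not show absence of added value, and that a positive result may partly reflect a second noisy reading.
3. **Descriptive.** Where questionnaire items are comparable, report the share of B and D plans that differ between the 2D and 3D questionnaires, with a 95% interval, noting that re-planning variation without 3D is not measured. For an assumed share of 30%, the Wilson interval is 18–45% at n = 40 and 21–41% at n = 80.
4. **Other correlations.** Label them exploratory and give intervals.

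The cost is wording and computation on data already scheduled; no extra patients or visits are needed. Item 3 depends on questionnaire content that the documents do not show. The downside is that fewer parameters will be called significant and the intervals will be wide.
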